# 1. ABBREVIATIONS AND DEFINITIONS

AE	Adverse Event
A(D)R	Adverse (Drug) Reaction
CRB	Cerebrolysin
CRF	Case Report Form
CRO	Contract Research Organisation
СТ	Computed tomography
DLPFC	Dorso-lateral pre-frontal cortex
FSNN	Foundation for the Study of Nanoneurosciences and
	Neuroregeneration
GCP	Good Clinical Practice
ICH	International Conference for Harmonization
IEC	Independent Ethics Committee
IMP	Investigational Medicinal Product
IV	Intra-venous
mL	Milli Liter
MMSE	Mini-Mental State Examination
MoCA	Montreal Cognitive Assessment Scale
MRI	Magnetic Resonance Imaging
PLC	Placebo
SAE	Serious Adverse Event
SAP	Statistical Analyses Plan
SAR	Serious Adverse Reaction
SESAR	Suspected Expected Serious Adverse Reaction

SOP	Standard Operating Procedure
SmPC	Summary of Product Characteristics
SUSAR	Suspected Unexpected Serious Adverse Reaction
WAIS	Wechsler Adult Intelligence Scale
WHO-UMC	World Health Organization-Uppsala Monitoring Center

# 2. PROTOCOL SUMMARY / SYNOPSIS

Coordinator	FSNN – Foundation for the Study of Nanoneurosciences and Neuroregeneration
Title	A Randomized, Placebo-controlled, double-blind trial to asses the effficacy and safety of CEREBROLYSIN in the treatment of Post-Stroke Cognitive Decline
Study Code	CODEC
Study Location	Institutul RoNeuro Cluj-Napoca
Investigational Medicinal Product	Cerebrolysin Solution for Injection (CRB)
Name of Active Substance	Cerebrolysin Concentrate
Phase	IV
Indication	Acute Ischeamic Stroke
Study Design	Randomized, double-blind, phase IV study
Study Duration	Study start: 05/2020 Study end: 12/2025
Sample Size	
 
Group 1 – Cerebrolysin N = 145
 
Group 2 – Placebo N = 145
 

Primary Objective	To assess the efficacy of Cerebrolysin versus Placebo upon a battery of co-primary neurocognitive outcome scores at 180 and 360 days after baseline.
Secondary Objectives	To assess the efficacy of Cerebrolysin versus Placebo upon neurological deficit, functional outcome, symptoms of anxiety and depression, drug safety and quality of life 180 and 360 days after baseline.
Primary Variables	The following psychometric tests are included in the primary mutivariate analysis (combined cognitive outcome measures):
	Strooptest(Stroop)Trail-Making-TestPartA(TMT-A)Digit Span Backwards Task (DS-BW)Verbal Fluency Test – CFL Version (VFT-CFL)DigitSymbol(DS-WPSI)Rey Auditory Verbal Learning Test (RAVLT)
Secondary Variables	Montreal Cognitive Assessment (MOCA)

	NIH	Stroke	Scale	(NIH)
	Modified	Rankin	Scale	(mRS)
	Hospital Anz	kiety and Depress	sion Scale (HADS	5)
	EQ-5D-5L			
Safety Variables	Adverse	E	vents	(AE)
	Severe Adv	erse Events (SAE	Ξ)	
Inclusion Criteria	
 
Diagnos PACS), 0
 
Onset of
 
NIH Stro admission
 
Pre-strol
 
No cogn score ≤
 
Age betw
 
Patient is the duration
 
	is of stroke, ische confirmed by MR Stroke within 72 oke Scale score on ke mRS of 0 or 1 itive impairment p 3 veen 40 and 80 y willing and able to on of the study	mic in origin (TAG hours prior to scr between 5-15 prior to stroke with ears, inclusive comply with the pr	CS or reening at inpatient an IQ code rotocol for
Exclusion Criteria	
 
Previous hemorrha
 
Severe psychom
 
Pre-exis Parkinsco
 
Pre-exis as majo or deme
 
History of Advance
 
Atermin
 
Pregnan
 
Any conti
 
Current of Dementi
 
Major of Kaplan S
 
Aphasia
 
Treatme last 30 d
 
Severe of
 
	symptomatic isclage not related to the visual or hearing the tric test proceduting and active material and	haemic stroke or he index stroke impairment inter- ures ajor neurological of epsy) ajor psychiatric dis- hizophrenia, bipol hol or drug abuse ardiac, or pulmon- osis with survival of cerebrolysin her therapeutic si- index stroke efficits with a Go 2 em 9 score of $\geq 2$ sin or Neuroprotect ISE Score <12	intracranial erfering with disease (eg. sease, such lar disease, ary disease < 1 year tudy bodglass & 2 ctants in the
Visit Schedule	Study Demogra Medical IQ code NIH Stro admissic mRS / pr	Visit 1 - Scr day -30 – within aphic data history and risk fa ke Scale score on remorbid mRS	reening Part 1 72 h after stroke actors between 5-15 a	e onset at inpatient

STUDY	Code:	CODEC

	In/Exclusion criteria – Part 1
	Visit 2 - Screening Part 2 & Baseline Study Day 1
	
 
Informed Consent (signed up to Visit 2 start)
 
Goodglass-Kaplan Communication Scale
 

	
 
MMSE
 
In/Exclusion criteria – Part 2
 
Pandomization
 

	
 
Primary Outcome Measures Stroop, TMT-A, DS-BW, VFT-CFL, DS-WPSI, RAVLT
 
Secondary Outcome Measures NIH, mRS, HADS, MoCA, EQ-5D-5L
 

	Safety Information
	Visit 3 - Efficacy & Safety Evaluation Study Day 180
	
 
Primary Outcome Measures Stroop, TMT-A, DS-BW, VFT-CFL, DS-WPSI, RAVLT
 
Secondary Outcome Measures NIH, mRS, HADS, MoCA, EQ-5D-5L
 
Safety Information
 

	Visit 4 - Efficacy & Safety Evaluation Study Day 360
	
 
Primary Outcome Measures Stroop, TMT-A, DS-BW, VFT-CFL, DS-WPSI, RAVLT
 
Secondary Outcome Measures NIH, mRS, HADS, MoCA, EQ-5D-5L
 
Safety Information
 

Investigational Product	Cerebrolysin Solution fo Injection (CRB): 30 ml diluted with 0.9% saline solution to 250 ml, administered by IV infusion
Reference Product	Placebo: 250 ml 0.9% saline solution administered by IV infusion
Treatment Schedule	Once daily IV infusions of either 30ml CRB or PLC
	Treatment Cycle 1Studyday1-1010 Infusions, once daily
	Treatment Cycle 2Studyday10 Infusions, once daily
	Treatment Cycle 3 Study day 121-130 10 Infusions, once daily

٦

Treatment Cycle	4	
Study	day	241-250
10 Infusions, o	nce daily	

\*All treatment cycles and efficacy evaluations will be performed within a window of ±3 working days.

#### 3. INTRODUCTION

#### 3.1. Background information

Stroke is the second leading cause of death and a major cause of disability worldwide. Its incidence is increasing due to aging population. In addition, more young people are affected by stroke in low- and middle-income countries. Ischemic stroke is characterized by the sudden loss of blood circulation to an area of the brain, resulting in a corresponding loss of neurologic function. Acute ischemic stroke is caused by thrombotic or embolic occlusion of a cerebral artery and is more common than hemorrhagic stroke.

Post-stroke cognitive impairment is a particularly serious consequence of cerebral ischaemia and often inhibits or retards patient rehabilitation. Post-stroke cognitive impairment occurs frequently in patients with stroke. The prevalence of post-stroke cognitive impairment ranges between 20-80%. The risk of post-stroke cognitive impairment is related to both demographic factors like age, education, occupation and vascular factors. The underlying mechanisms PSCI are not fully understood.

However, scientific literature has shown that neuroanatomical lesions caused by stroke on strategic areas such as the hippocampus and white matter lesions, cerebral microbleeds due to the small cerebrovascular diseases and the mixed AD with stroke, alone or in combination, contribute to the pathogenesis of post-stroke cognitive impairment.

Current treatments for PSCI do not improve long-term outcomes for a significant proportion of patients and leave substantially unmet medical needs. Initiatives to address the challenge of post-stroke rehabilitation have included therapies that modify multiple pathogenetic mechanisms and provide protection to neural networks and facilitate their regeneration. Promising biological agents have been tested, but few have so far yielded clinically conclusive evidence, further emphasising the shortage of therapies available to treat this disease. Due to the heterogenous results of clinical studies, additional research is need to determine the efficacy of various therapeutic strategies.

#### 3.2. Study Rationale

Incident stroke alters a patient's cognitive trajectory, and this effect is greater with increasing age and cardioembolic stroke. About one-third of stroke patients have significant cognitive impairment within several months of the event. In addition, silent strokes, experienced by 1 in 10 adults by their early 60s, are harbingers of both future stroke and cognitive dysfunction.

Researchers from the University of Michigan tracked the trajectories of cognitive decline before and after incident stroke in a prospective study of 23,572 participants age 45 years or older without baseline cognitive impairment (Levine et al., 2015). The results show that stroke was associated with acute decline in global cognition, new learning, and verbal memory. Participants with stroke, compared with those without stroke, demonstrated faster

declines in global cognition and executive function, but not in new learning and verbal memory, compared with pre-stroke slopes. These findings suggest that clinicians may have an opportunity to intervene immediately following stroke to prevent accelerated stroke-related cognitive decline.

The neuroprotective adjuvant effect of Cerebrolysin in prevention of postoperative cognitive disfunction has been documented for cardiac (Polushin et al., 2017) and neurosurgical (Matula & Schoeggl, 2000) procedures. Furthermore, the drug has been proven to stabilize cognitive decline and aid in regression of cognitive disorders predicting vascular dementia in a randomized double-blind placebo-controlled trial (Vereshchagin et al., 2001). In a clinical-electrophysiological study of 40 patients, courses of cerebrolysin treatment decreased the severity of memory and attention impairments, improving the overall cognitive status of patients with cerebral vascular insufficiency (Damulin, Koberskaya, & Mkhitaryan, 2008).

The rationale of the study is based on the previously documented neuroprotective characteristics of Cerebrolysin with potential of preventive effects for cognitive decline after stroke.

#### 4. STUDY OBJECTIVES

This study shall assess the efficacy of pharmacological intervention with Cerebrolysin in the prevention of post stroke cognitive decline.

The aim of this trial is to test the hypothesis that patients randomized to Cerebrolysin show improved cognitive outcome measured with a battery of co-primary neuropsychological tests as compared to patients randomized to placebo (multivariate analysis of combined cognitive outcome measures).

Furthermore, it is intended to investigate the hypothesis that Cerebrolysin, as compared to placebo, will show improved scores at four, seven and thirdteen months post-stroke on neurological deficit, global function, depression and anxiety. In addition, it is intended to investigate the effects of Cerebrolysin versus Placebo on the Quality of Live at seven and thirdteen months after stroke. Furthermore, it is intended to evaluate the safety of Cerebrolysin in patients with recent stroke and to determine which demographic, clinical and radiological characteristics predict response to treatment with Cerebrolysin.

Other study designs, including non-randomised controlled trials, can detect associations between an intervention and an outcome. But they cannot rule out the possibility that the association was caused by a third factor linked to both intervention and outcome. Random allocation ensures no systematic differences between intervention groups in factors, known and unknown, that may affect outcome. Double blinding ensures that the preconceived views of subjects and clinicians cannot systematically bias the assessment of outcomes. Intention to treat analysis maintains the advantages of random allocation, which may be lost if subjects are excluded from analysis through, for example, withdrawal or failure to comply. Meta-analysis of controlled trials shows that failure to conceal random allocation and the absence of double blinding yield exaggerated estimates of treatment effects.

#### 4.1. Primary Objective

It is the primary objective of this clinical study to assess the efficacy of Cerebrolysin versus Placebo upon a battery of co-primary neurocognitive outcome scores at 180 and 360 days after baseline (7 and 13 months after the onset of ischeamic stroke).

#### 4.1.1. **Primary Variables**

The following psychometric tests are combined by multivariate analysis with their score changes from baseline at 180 and 360 days after baseline (7 and 13 months after the onset of ischeamic stroke):

- Stroop Color Word test (Stroop)
- Trail-Making-Test Part A (TMT-A)
- Digit Span Backwards Task (DS-BW)
- Digit Symbol (DS-WPSI)

- Verbal Fluency Test CFL Version (VFT-CFL)
- Rey Auditory Verbal Learning Test (RAVLT)

#### 4.2. Secondary Objectives

It is the secondary objective of this clinical study to assess the efficacy of Cerebrolysin versus Placebo upon neurological deficit, functional outcome, symptoms of anxiety and depression, drug safety and quality of life at 180 and 360 days after baseline (7 and 13 months after the onset of ischeamic stroke).

#### 4.2.1. Secondary Variables

- Score and score changes from baseline of the individual primary outcome scales at 180 and 360 days after baseline (7 and 13 months after the onset of ischeamic stroke)
- Score and score changes from baseline NIH Stroke Scale at 180 and 360 days after baseline
- Score and score changes from baseline Modified Rankin Score at 180 and 360 days after baseline
- Score and score changes from baseline Hospital Anxiety and Depression Scale at 180 and 360 days after baseline
- Score and score changes from baseline EQ-5D-5L at 180 and 360 days after baseline
- Safety parameters including Adverse Events at 180 and 360 days after baseline

#### 5. STUDY DESIGN

Randomized, double-blind study design

One dose group (Cerebrolysin 30ml) shall be tested against placebo. The two study groups are therefore:

Study Group 1:	30ml Cerebrolysin
Study Group 2:	Placebo (0.9% NaCl)

The trial will be conducted in subjects suffering from ischemic stroke in the anterior circulation, either TACS or PACS. The diagnosis of the ischemic stroke as well as the location of the stroke will be determined clinically and confirmed by neuroimaging.

The study extends over an observation period of 390 days. Five visits for clinical evaluation are planned for the following points in time:

**Visit 1 (Study Day -30±3 working days) – Screening Part 1** is scheduled within 72h after the onset of stroke and is followed by a  $30 \pm 3$  working days run-in period for the patients. **Visit 2 - Screening Part 2 & Baseline Evaluation** is scheduled at study day 1. Following to the baseline assessment, study participants shall begin with Treatment Course 1 comprising ten once daily infusions of study medication on study days 1 to 10. Following a treatment free period of one month, patients shall receive Treatment Course 2 comprising ten once daily infusions of study medication on study days 61-70 and again after a break of one months Treatment Course 3 on study days 121-130. **Visit 3 – Efficacy & Safety Evaluation** which is scheduled for study day 180. The final **Visit 4 – Efficacy & Safety Evaluation** which is the primary endpoint of the study is scheduled for study day 360 post stroke. All treatment cycles and efficacy evaluations will be performed within a window of ±3 working days.

The study shall be initiated in May 2020. The first patient at each participating center should be enrolled within 2 months of initiation. The duration of the study is expected to be 4 years.

Clinical Study Phase: Phase IV

#### 6. SELECTION AND WITHDRAWAL OF PATIENTS

#### 6.1. Patient Inclusion Criteria – PART 1 / DAY -30

- Onset of Stroke within 72 hours prior to screening
- NIH Stroke Scale score between 5-15 at inpatient admission
- Pre-stroke mRS of 0 or 1
- No cognitive impairment prior to stroke with an IQ code score  $\leq 3$
- Age between 40 and 80 years, inclusive
- Patient is willing and able to comply with the protocol for the duration of the study

#### 6.2. Patient Exclusion Criteria – PART 1 / Day -30

- Previous symptomatic ischaemic stroke or intracranial hemorrhage not related to the index stroke
- Severe visual or hearing impairment interfering with psychometric test procedures
- Pre-existing and active major neurological disease (eg. Parkinson's Disease, Epilepsy)
- Pre-existing and active major psychiatric disease, such as major depression, schizophrenia, bipolar disease, or dementia
- History of significant alcohol or drug abuse
- Advanced liver, kidney, cardiac, or pulmonary disease
- A terminal medical diagnosis with survival < 1 year
- Pregnancy or lactating
- Any contraindications to Cerebrolysin
- Current enrolment in another therapeutic study

#### 6.3. Run-In Period – Day -30 to Day 1

During the Run-in-Period, the patient the patient shall received standard stroke care and the treatment administered will be recorded. Patients shall not receive Cerebrolysin treatment or treatment neuroprotective drugs during this period. Furthermore, an MRI will be performed before the study baseline visit.

#### 6.4. Patient Inclusion Criteria – PART 2 / DAY 1

- Signed Informed Consent
- Patient continues to fulfill in- and exclusion criteria PART 1
- Diagnosis of stroke, ischemic in origin (TACS or PACS), confirmed by MRI

#### 6.5. Patient Exclusion Criteria – PART 2 / Day 1

- Dementia due to strategic index stroke
- Major communication deficits with a Goodglass & Kaplan Score lower than 2
- Aphasia with an NIHSS Item 9 score of  $\geq 2$
- Treatment with Cerebrolysin or Neuroprotectants in the last 30 days
- Severe dementia with MMSE Score <12

#### 6.6. Stopping and Discontinuation Criteria

#### 6.6.1. Discontinuation Criteria related to the Study

- Insufficient recruitment
- Continuous serious protocol violation and deviation

#### 6.6.2. Discontinuation Criteria related to the Patient

Patients will be advised in the Informed Consent Forms that they have the right to withdraw from the study at any time without prejudice and may be withdrawn at the Investigator's / Coordinator's discretion at any time. In the event that a patient drops out of the study or is withdrawn, the withdrawal / study termination page in the CRF should be completed. On the withdrawal page the Investigator should record the date of the withdrawal, the person who initiated withdrawal and the reason for withdrawal. Reasonable effort should be made to contact any patient lost to follow up during the course of the study in order to complete assessments and retrieve any outstanding data and study supplies.

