#### Withdrawn by the Investigator due to

- Serious Adverse Drug Reaction
- Lack of efficacy
- Consent withdrawn
- Administrative reasons

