#### The patient or his/her representative requested withdrawal due to

- An Adverse Event for which the Investigator did not consider removal from the study
- Perceived insufficient therapeutic effect.
- Withdrawal of consent for any other reason (data recorded until withdrawal will be kept in the database if not explicitly denied by the patient)

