#### 13.12.3. Full Analysis Set (FAS)

FAS population is defined as all patients who have no "severe" violation of entry criteria, had at least one dose of medication and at least one post-baseline observation of at least one primary efficacy criterion (definition according to ICH E9 § 5.2. Analysis Sets). FAS population will be used for all efficacy analyses.

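### Withdrawal for a drug reaction or lack of effect is handled as leaving the study, and nothing requires these patients to attend the cognitive assessments at Visits 3 and 4

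*Protocol*

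**What the plan says.** **Withdrawal (6.6.2).** If "a patient drops out of the study or is withdrawn, the withdrawal / study termination page in the CRF should be completed". The investigator's reasons include "Serious Adverse Drug Reaction" and "Lack of efficacy". The patient's reasons include "Perceived insufficient therapeutic effect" and "An Adverse Event for which the Investigator did not consider removal from the study"; the last of these shows that removal means removal from the study. For withdrawn consent, "data recorded until withdrawal will be kept in the database if not explicitly denied by the patient". The only instruction to seek outstanding assessments is written for patients lost to follow-up.

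**Stopping study drug (10.5).** Patients who stop because of adverse experiences are treated and followed medically, with the outcome entered in the CRF. The cognitive visits are not mentioned.

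**Timing (5, 7.1.1, 11.1).** Infusion courses run on days 1-10, 61-70, 121-130 and 241-250. Efficacy is tested at baseline, day 180 (Visit 3) and day 360 (Visit 4).

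**Analysis set (13.12.3).** The full analysis set (FAS) requires "at least one post-baseline observation of at least one primary efficacy criterion".

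**Missing data (13.11.2 to 13.11.4).** Stroke-related inability to do a test (code 2) receives the worst score. Any other reason (code 3) is filled by last percentile carried forward (LPCF), but only from an earlier follow-up value; without one the scale stays missing.

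**Stated principle (4).** "Intention to treat analysis maintains the advantages of random allocation, which may be lost if subjects are excluded from analysis"; withdrawal is one of the examples given.

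**The concern.** A serious drug reaction, lack of efficacy and perceived lack of effect are consequences of treatment or of outcome. If they end a patient's participation, the resulting missing data are informative and may differ between arms. The 15% enhancement of the sample size in section 13.8 replaces lost numbers; it does not remove a bias.

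The data concerned could mostly be collected. A patient who is off infusions may well be able to sit the tests at two visits that are already scheduled. An analysis plan written later cannot recover assessments that the protocol never asked for, so this has to be settled in the protocol.

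**Working it through.** **What happens to a withdrawn patient**

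| Time of withdrawal | Day-180 value | Day-360 value | FAS |
|---|---|---|---|
| Before day 180, not tested later, code 3 | missing, no LPCF possible | missing, no LPCF possible | outside |
| Before day 180, code 2 applies | worst score assigned | worst score assigned | 13.12.3 does not say whether an assigned score counts as an observation |
| After day 180 | observed | imputed | inside |

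A patient withdrawn for a drug reaction would ordinarily not meet code 2. Three of the four infusion courses fall before day 180.

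**The plan's own sample size (13.8)**

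Inputs: two-sided alpha 0.05, power 90%, Mann-Whitney statistic (MW) 0.60, correlation 0.6, and six scales from 13.3.2.

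- Noether formula for one scale: (1.96 + 1.2816)² / (6 × 0.10²) = 175.1 per arm.
- Factor for averaging six equally correlated scales: (1 + 5 × 0.6)/6 = 0.667, giving 117 evaluable per arm.
- With 15% added: 117/0.85 = 138, or 117 × 1.15 = 135.

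The stated 145 is therefore not reproduced exactly. The separate sample size document cited in 13.8 is not at hand. Taking 145 × 0.85 = 123 evaluable per arm, power for six scales is 91.4%, so the stated size is slightly conservative. Nothing below depends on this difference.

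**Illustration 1: extreme case, no true effect, 123 per arm**

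Assume that all excess withdrawals in one arm would have ranked at the very bottom on all six scales.

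- SE of the average MW = √[0.667 / (6 × 123)] = 0.0301.
- Removing the bottom share p of one arm moves MW by 0.5p.
- Two-sided rejection = Φ(−1.96 + shift/SE) + Φ(−1.96 − shift/SE).

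| Difference between arms | Shift in MW | Two-sided error |
|---|---|---|
| 0 points | 0 | 5.0% |
| 2 points | 0.010 | 6.3% |
| 3 points | 0.015 | 7.9% |
| 5 points | 0.025 | 13.2% |

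A shift of 0.025 is a quarter of the design effect of 0.60 − 0.50 = 0.10.

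**Illustration 2: withdrawal partly related to outcome**

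Simulation with 145 randomised per arm, six normal scales, correlation 0.6 and 3,000 repetitions. Patients are removed by a score correlated about 0.7 with their average outcome. That correlation and the removal rates are assumptions.

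| True MW | Removed, Cerebrolysin / placebo | Mean MW | Two-sided rejection |
|---|---|---|---|
| 0.50 | 0% / 0% | 0.501 | 5.4% |
| 0.50 | 5% / 0% | 0.516 | 8.9% |
| 0.50 | 10% / 5% | 0.514 | 9.0% |
| 0.50 | 15% / 10% | 0.515 | 8.8% |
| 0.50 | 15% / 5% | 0.528 | 19.5% |
| 0.50 | 5% / 15% | 0.472 | 18.5% |
| 0.60 | 0% / 0% | 0.600 | 95.3% |
| 0.60 | 15% / 15% | 0.607 | 95.5% |
| 0.60 | 5% / 15% | 0.577 | 77.3% |

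Equal removal from both arms leaves power almost unchanged. The harm comes from the imbalance, not from the loss of numbers.

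**The case against.** The protocol has more in place than section 6.6.2 alone suggests, and a reader might infer too much from that section.

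- *That leaving the study is the only way to stop.* The documents do not support this. Section 10.5 names patients who discontinue study drug, the FAS requires only one dose, and section 13.14 excludes patients below 80% compliance from the per-protocol analysis only. Under-treated patients can remain in the study and the FAS. What stands is that 6.6.2 does not refer to this status and 10.5 does not attach the cognitive visits to it.
- *That every withdrawn patient loses both visits.* Both are lost only if withdrawal comes before day 180. No efficacy test is scheduled between baseline and day 180, so withdrawal for lack of efficacy is at least as plausible at or after Visit 3, when FAS membership is already secured.
- *That informative dropout is ignored.* Section 13.11 gives the worst score for stroke-related inability and intends deaths to rank worst. These rules cover many of the patients likely to do badly, but not a patient withdrawn early for another reason.
- *That 13% is the expected error rate.* It is an extreme bound. A drug reaction does not imply bottom cognitive rank, and the protocol gives no withdrawal rates by arm.
- *That the bias favours Cerebrolysin.* If the drug works, withdrawals for lack of efficacy should fall more on placebo and bias against it.
- *That testing withdrawn patients is forbidden.* It is not; it is simply not required. The sentence about the termination page is administrative. The withdrawal reasons, with 13.11.4 and 13.12.3, carry the point.

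The passage on intention to treat in section 4 concerns exclusion from analysis. It still applies, because the FAS rule turns an uncollected day-180 assessment into exactly such an exclusion.

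**Conclusion.** The point holds in this limited form. Section 6.6.2 handles treatment-related and outcome-related withdrawal as leaving the study, and no section requires those patients, or those who stop study drug under 10.5, to attend Visits 3 and 4. Withdrawal before day 180 without later testing puts a patient outside the FAS unless the stroke-related code applies; withdrawal after day 180 replaces the observed day-360 value by an imputed one. This departs from the principle that section 4 sets out.

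The size cannot be known from the protocol. Under the stated assumptions, a 5-point imbalance takes two-sided error from 5% to about 9%, or about 13% in the extreme case; a 2-point imbalance in the extreme case gives about 6%. With a true MW of 0.60 and 10 points more poor responders lost on placebo, power falls from about 95% to about 77%. The change should be made because the bias is credible and cheap to avoid, not because a particular error rate has been shown.

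**What to change.** In section 6.6.2, with a cross-reference in section 10.5, separate stopping study infusions from leaving the study:

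- Patients who stop infusions or are withdrawn from treatment, and have not refused follow-up, still attend Visits 3 and 4 and are analysed as randomised.
- The study termination page is used only for refusal of further follow-up, loss to follow-up or death.
- The reasons for stopping treatment are unchanged.

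Patients who then attend Visit 3 supply the post-baseline observation that section 13.12.3 asks for, so they enter the FAS under its present definition.

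The cost is protocol and CRF wording, plus some site effort to bring back patients who are off treatment. Both visits are already in the schedule.
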